One focus of the investigator meetings will be to continuously monitor and develop strategies to prevent adverse reactions, monitor the research staff, and protect data integrity. Accrual data will be reviewed by the team and the UTHealth IRB. The study team will make amendments to the protocol should accrual fall below 15% of the target, or should drop-outs exceed projections by 15%. This will include the addition of recruitment sites.

Statistics

Randomization. Participants will be randomly assigned to the intervention or wait list control arm using a computer-generated blocked 2:1 allocation; 300 participants will be in the intervention arm and 150 will be in the wait list control arm (see Figure 3). Participants will be told which group they are in after completing the baseline survey and will receive a study-issued phone with programmed YEH resources unless they prefer to use their own phone. In this case, the behavioral feedback app will be loaded onto their personal phone for those in the intervention arm, and these youth will be provided with a list of YEH services.

Study Design.

| | Baseline | Intervention | 3 Mon. | 6 Mon. | 9 Mon. | Intervention |
|-------------------|----------------|------------------|----------------|----------------|----------------|--------------|
| Treatment arm | O ₁ | X O ₂ | O ₃ | O ₄ | O ₅ | |
| Wait list control | O ₁ | O ₂ | O ₃ | O ₄ | O ₅ | X |

Sample Size and Power Calculations. The primary endpoint is the efficacy of NCM to increase PrEP and nPEP uptake, HIV testing, STI screening, and condom use. Conservatively assuming an attrition rate of 30% at 9 months, the final sample size will be 315, with the 2:1 randomization allocation providing for 210 participants in the intervention arm and 105 in the control arm. We estimate a retention rate of 70% based on study resources, community partnerships and support, the use of study-issued phones, the use of increasing follow-up incentives. This retention rate is substantially lower than the rate reported for other longitudinal YEH studies that have retained 88-89% ^{13,14} of youth to be very conservative in our retention estimation.

Table1. Outcome Measures by Study Aim

| Construct | Scale/Measure | Alpha |
|-----------------------|---|-------|
| Aim 1 Outcomes | | |
| PrEP/nPEP Uptake | PrEP uptake; nPEP uptake (NCM report, chart review) | NA |
| Condom Use | Youth Risk Behavior Survey; ¹ (condom use at last sex) | NA |

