| HIV/STI Test Uptake | Rapid HIV test; Gonorrhea, Chlamydia, Syphilis test | NA |
| Aim 2 Outcomes | | |
| Mental Health | Brief Symptom Index-18 ^{2,3} | 0.80 |
| Housing Status | In a shelter, apt/house, with someone, outside, in a car...? | NA |
| Substance Use | TCU Drug Screen II ^{4,5} | 0.89 |

| Exploratory Outcomes (possible mediators based on CHSCF; see Figure 1) | | |
|--|---|------|
| Healthcare Engagement | Healthcare clinic visit adherence ⁶ | NA |
| Condom Use Self-Efficacy | Condom Use Self-Efficacy Scale ⁷ | 0.91 |
| HIV Risk Perception | Perceived Risk of HIV scale ⁸ | 0.88 |
| PrEP Facilitators & Barriers | Facilitators and Barriers to PrEP Use ⁹ | NA |
| Health Seeking | General Help Seeking Questionnaire ¹⁰ | 0.83 |
| Coping | Coping Inventory for Stressful Situations-Adolescent ^{11,12} | 0.92 |

For Aim 1, we anticipate having 87% power (95% CI: 84.8, 89.0) to detect the intervention effect on the reduction of condomless sex. Alpha was set at .05 and the power calculation was conducted using the SIMR package¹⁵ by 1000 Monte Carlo simulations with a generalized linear mixed model design that included a random intercept per participant. Data for the simulation were generated with compound symmetric covariance structure in the SIMSTUDY package by assuming that 79% of participants are sexually active and the probability of condomless sex will reduce modestly from 0.7 to 0.4 in the intervention group. The probability was conservatively assumed to decrease to 0.55 in the control group due to the potential for a placebo and/or contamination effect. The effect sizes and powers for HIV testing and STI screening and treatment outcomes are anticipated to be of similar magnitude to the condomless sex outcome. For the PrEP uptake outcome, it was assumed that rates would change from 2% to 4% in the control group and to 24% in the intervention group, for which the simulation resulted in 99% power (95% CI: 94.6, 99.9). Power analysis for the continuous instrument scores of Aim 2 indicates that a sample size of n = 315 will provide 80% power for the interaction of time and arm in a repeated measures model when the effect size is f= .11, a small effect size. This calculation assumes a correlation between repeated measures of r = .50.

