Analysis Plan by Study Aim. Descriptive statistics will be calculated by study arm for baseline demographic characteristics, including age, gender identity, race/ethnicity, sexual orientation, educational level, and employment. However, random allocation of the participants to the intervention and control study arms will make it unlikely that there will be significant differences between the groups for baseline variables that could confound the results. Descriptive statistics will be calculated for all measures at each time point. We expect missing data to be minimal. Obvious errors will be corrected; those that cannot, will be set to missing. Missing data on the instruments will be replaced using single imputation with case mean substitution (i.e., replacing a participant's missing items with that participant's mean item score).¹⁶ Reliability estimates of the study instruments will be computed with Cronbach's alpha ($\geq .70$ will be considered acceptable for internal consistency).¹⁷ Analysis for this study will be based on the intent-to-treat principle.¹⁸ **Aim 1:** Generalized estimating equation (GEE) analysis will be used to compare the groups' changes over time in the dichotomous outcomes - PrEP uptake, nPEP uptake, condom use, and HIV/STI testing – assessed immediately post intervention and at 3-, 6-, and 9-months. The effects to be tested in the model will include time, study arm, and the interaction of time and study arm. **Aim 2:** GEE with normal distribution and identity link will be used to compare the intervention arm to the control arm over time with respect to mental health symptoms measured with the Brief Symptom Index, substance use, and number of homeless days in the past month. In case distributional assumptions are not met, Poisson link may be used for the number of homeless days and substance use days. The effects to be tested will include time, study arm, and the interaction of time and study arm. Time will be treated as a continuous variable unless nonlinearities are present, in which case it will be treated as a categorical variable. Hypothesis 1: Intervention youth will have increased PrEP/nPEP uptake and adherence, condom use, STI/HIV testing and treatment compared to wait list control youth. Hypothesis 2: YEH Intervention youth will have decreased mental health symptoms and substance use and report fewer nights on the street compared to waitlist control youth. **Exploratory Aim:** To explore for mediation of the variables in the Comprehensive Health Seeking and Coping Framework,

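### Five outcomes share the primary endpoint with no order, multiplicity adjustment or win rule; if any one success at two-sided .05 counted, the false-benefit risk would be about 7-12% rather than 2.5%

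*Combined protocol and SAP*

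**What the plan says.** All references are to the combined protocol and SAP.

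- **Primary endpoint** (Statistics, Sample Size and Power Calculations), as the plan words it: "The primary endpoint is the efficacy of NCM to increase PrEP and nPEP uptake, HIV testing, STI screening, and condom use". Counted singly, these are PrEP uptake, nPEP uptake, HIV testing, STI screening and condom use.
- **Alpha** (same section): "Alpha was set at .05 and the power calculation was conducted" by simulation. Sidedness is not given, and nothing says whether .05 applies to each outcome or to the set.
- **Power** (same section): condomless sex comes first, at 87% (95% CI 84.8 to 89.0). PrEP uptake is the other simulated Aim 1 outcome, "for which the simulation resulted in 99% power (95% CI: 94.6, 99.9"). For the testing outcomes there is only an expectation: "The effect sizes and powers for HIV testing and STI screening and treatment outcomes are anticipated to be of similar magnitude" to condomless sex. nPEP uptake has neither an assumed rate nor a power figure.
- **Analysis** (Analysis Plan by Study Aim, Aim 1): GEE compares the arms' "changes over time in the dichotomous outcomes", listed as "PrEP uptake, nPEP uptake, condom use, and HIV/STI testing", with the timing given as "assessed immediately post intervention and at 3-, 6-, and 9-months". Then: "The effects to be tested in the model will include time, study arm, and the interaction of time and study arm".
- **Hypothesis** (Objectives, H1): intervention youth are expected to improve more on these outcomes over 9 months than controls.

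Neither the Statistics section nor any other supplied section ranks the outcomes, splits alpha, defines a composite or co-primary set, or says how many outcomes must succeed.

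**The concern.** A primary endpoint made of several outcomes needs a rule that turns several results into one conclusion. Without it, the team could test each outcome at .05, find one significant, and report the trial as positive on its primary endpoint without departing from the written plan. The error rate of that conclusion would exceed that of the single .05 test used for sizing. The meaning of a positive trial matters here, because the Innovation section ties national dissemination to the intervention proving efficacious.

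**Working it through.** **1. The plan's own figures.** 450 × (1 − 0.30) = 315; 300 × 0.70 = 210; 150 × 0.70 = 105. These match. The interval 84.8 to 89.0 is the exact binomial interval for 870 successes in 1000 simulations. The 87% itself cannot be confirmed or refuted, because the tested term, the within-person correlation and the shape of change over time are not given. A simulated linear arm × time test at 210/105 gave 58% to 81% for assumed latent correlations .3 to .9. The 87% is therefore used below only as illustration.

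**2. Error if any one success counts.** Assumptions: one test per outcome, each at two-sided .05, only benefit counted (.025 per test), all nulls true. With k independent tests the risk is 1 − 0.975^k:
- k = 1: 2.5%
- k = 4: 1 − 0.975^4 = 9.6%
- k = 5: 1 − 0.975^5 = 11.9%

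The documents give no correlation between outcomes, so equicorrelated normal test statistics were integrated over an assumed range:

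| Tests | ρ = 0 | .3 | .5 | .7 |
|---|---|---|---|---|
| 4 | 9.6% | 8.7% | 7.8% | 6.5% |
| 5 | 11.9% | 10.5% | 9.2% | 7.4% |

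Four tests applies if HIV and STI testing are one variable, as the Aim 1 list could be read, or if nPEP uptake leaves the family.

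**3. Error if all must succeed.** The chance that every outcome is falsely positive cannot exceed the 2.5% for any one of them, so there is no inflation.

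**4. Illustrative power under a rule.** The noncentrality for 87% power is 1.960 + 1.126 = 3.086.
- Fixed sequence, condom use first: 87%.
- Fixed sequence, condom use second after PrEP uptake: 0.99 × 0.87 = 86.1% (independent tests).
- PrEP uptake: 99% if first; 0.87 × 0.99 = 86.1% if second after condom use.
- Holm over four (PrEP uptake, condom use, HIV testing, STI testing), power for condom use, 400,000 simulations: 84% (ρ = 0) to 82% (ρ = .7) if both testing outcomes also have 87% power, and 76% if neither has any effect. The last figure can be checked by hand. Once PrEP is rejected, condom use faces .05/3 with critical value 2.394, and Φ(3.086 − 2.394) = Φ(0.692) ≈ .755.

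**The case against.** **The plan does not say that any single success is enough.** This is the strongest reply, and it stands. The outcomes are joined by a plain conjunction, which can be read as requiring all of them or as a set of separate claims. The percentages therefore describe one permitted reading. The gap is that the plan does not choose. An all-must-succeed reading would also include nPEP uptake, so its power cannot be worked out from the documents.

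**The 2.5% reference is derived.** It comes from reading .05 as two-sided and counting benefit only. If .05 were one-sided, the reference would be 5% and five tests would give 13.5% (ρ = .7) to 22.6% (ρ = 0). The inflation remains.

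**There is an informal lead outcome.** Condomless sex opens the sizing, the testing outcomes are scaled to it, and the mediation plan names it as the outcome. This is useful evidence for choosing an order, but it is not a hierarchy.

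Three stronger readings go beyond the text:
- A reader might infer that the outcome set contradicts itself: five outcomes, four labels, three table rows. Much of this is grouping, since the table rows list their measures separately. It also means that three tests, with a floor near 5.5% at ρ = .7, is poorly supported. The real variation is narrower: STI treatment appears in Aim 1, and treatment and adherence in Hypothesis 1, but none is in the primary endpoint sentence.
- A reader might infer that the deciding test is wholly open. The wording on change over time and greater improvement points to arm × time, although no term is named as deciding.
- A reader might take the 87% as wrong. It cannot be confirmed, but it is not refuted.

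**Conclusion.** The point holds in conditional form. Five outcomes make up the primary endpoint, and the plan has no rule for order, adjustment or number of successes. If each is tested at two-sided .05 and any success counts, the chance of at least one false finding of benefit is about 7% to 12% for five tests and 6.5% to 9.6% for four, against 2.5% for one test. This rests on all nulls being true, one test per outcome, and an assumed correlation between .7 and 0. A higher correlation lowers the risk: five tests reach 5.5% only at about .87. The documents do not support saying that the trial will inflate its error, only that nothing written prevents it. The sponsor should correct this before results by arm are known.

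**What to change.** Before results by arm are seen, add to the SAP:

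1. **One contrast per outcome.** Name the deciding term. The text points to arm × time. Say whether baseline is included, since Objectives lists it and the Aim 1 analysis list starts immediately after the intervention.
2. **One rule controlling error at .05 across the Aim 1 primary outcomes**, with sidedness stated. Either:
   - a fixed sequence, in an order the sponsor chooses and justifies. PrEP uptake and condomless sex are the two with simulated power, and condomless sex leads the sizing; or
   - Holm over the same set.
3. **The status of nPEP uptake.** Decide whether it stays in the primary family. Moving it out changes a stated endpoint and should be recorded as such.
4. **What had been seen when the rule was set.** The Safety Monitoring Committee's quarterly reports include inferential results to date.

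**Cost.** The text is short, and no participants, visits or data are added. The stated power should be rechecked for the named contrast. In a sequence, outcomes after the first failed step are supportive only; Holm avoids defending an order but loses some power. Taking the stated 87% at face value, condom use keeps about 87% if first, 86% if second after PrEP uptake, and about 76% to 84% under Holm over four.

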Measures. The baseline survey will include demographics such as age, sex (operationalized as the gender identity, not biological sex), race/ethnicity, sexual orientation, educational level, and employment. We will assess historical factors to characterize the sample, such as foster care history, adverse childhood experiences, age at the first episode of homelessness, and duration of current homelessness, all of which have been linked to sexual risks.^{114,115} PrEP/nPEP uptake

will be assessed through NCM report and medical chart verification of PrEP/nPEP prescription. Follow-up surveys will assess condom use at last sex and during the past 3 months, substance use,¹¹⁶ sexual behaviors,¹¹⁷ HIV and STI testing, mental health symptoms,^{118,119} and housing status. In alignment with CHSCF, we will assess possible intervention mediators including healthcare engagement,¹²⁰ condom use self-efficacy,¹²¹ HIV risk perception,¹²² PrEP barriers/facilitators,¹²³ health seeking,¹²⁴ and coping^{125,126} using validated measures.

Outcome Measures by Study Aim

| Construct | Scale/Measure | Alpha |
|---|---|-------|
| Aim 1 Outcomes | | |
| PrEP/nPEP Uptake | PrEP uptake; nPEP uptake (NCM report, chart review) | NA |
| Condom Use | Youth Risk Behavior Survey; ¹²⁸ (condom use at last sex) | NA |
| HIV/STI Test Uptake | Rapid HIV test; Gonorrhea, Chlamydia, Syphilis test | NA |
| Aim 2 Outcomes | | |
| Mental Health | Brief Symptom Index-18 ^{118,119} | 0.80 |
| Housing Status | In a shelter, apt/house, with someone, outside, in a car...? | NA |
| Substance Use | TCU Drug Screen II ^{82,129} | 0.89 |
| Exploratory Outcomes (possible mediators based on CHSCF; see Figure 1) | | |
| Healthcare Engagement | Healthcare clinic visit adherence ¹²⁰ | NA |
| Condom Use Self-Efficacy | Condom Use Self-Efficacy Scale ¹²¹ | 0.91 |
| HIV Risk Perception | Perceived Risk of HIV scale ¹²² | 0.88 |
| PrEP Facilitators & Barriers | Facilitators and Barriers to PrEP Use ¹²³ | NA |
| Health Seeking | General Help Seeking Questionnaire ¹²⁴ | 0.83 |
| Coping | Coping Inventory for Stressful Situations-Adolescent ^{125,126} | 0.92 |

Study Population

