At-home tests will be available for Syphilis, Chlamydia, and Gonorrhea using commercially available Everlywell tests. Study staff will mail test kits in a discreet envelope or hand-deliver the kits at a convenient public location (e.g., grocery store). Participants will register the kits on a private, secure platform and mail samples to Everlywell lab in a postage-paid envelope. Participant will be able to access results online. In the event of a positive result, a third party provider via Everlywell will contact participant and offer referrals for treatment. Study staff will follow up on treatment and make appropriate reports to Houston Health Department. Study staff will acquire results via the secure Everlywell Lens platform.

Participants will receive an \$20 gift card for completing each STI testing follow up in addition to incentive for surveys to cover the cost of transportation and time.

If participants have been testing for HIV, chlamydia and gonorrhea, and/or syphilis in the last 2 weeks and report no potential exposure, study staff will ask permission to obtain results from a partnering agency outlined in the consent form.

Study staff will be equipped with PPE for all in-person visits in accordance with national (CDC & NIH), local (Harris County and City of Houston), and UTHealth clinical research guidelines.

Sharing test results. Participants who request written documentation of test results will be provided with the Research Results Letter. Research staff who conducted the test will fill out testers name, date, location, time, test(s) conducted and results. Letter will specify that test was conducted as part of a research study and provide study contact information.

PrEP sub study. Participants who initiate PrEP during the study will be invited to take part in a PrEP sub study which includes a medication adherence test and interview. Separate protocol and consent form will be used for the sub study.

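### PrEP uptake is analysed as a repeated yes/no at four visits, with no rule for scoring a visit and no named deciding term; the stated 99% power fits an arm contrast, not arm-by-time

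*Combined protocol and SAP*

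**What the plan says.** - **Measurement.** Measures (Study Design) assesses uptake by nurse case manager report and "medical chart verification of PrEP/nPEP prescription". The outcome tables repeat these sources. None of them gives a look-back window or a carry-forward rule.
- **Power.** Sample Size and Power Calculations states "Alpha was set at .05". On PrEP it says "it was assumed that rates would change from 2% to 4% in the control group and to 24% in the intervention group". The power reported for these inputs is 99%, with a 95% interval from 94.6 to 99.9. The method is described as "by 1000 Monte Carlo simulations with a generalized linear mixed model design that included a random intercept per participant".
- **Numbers.** Randomization specifies "computer-generated blocked 2:1 allocation; 300 participants will be in the intervention arm and 150 will be in the wait list control arm". With 30% attrition this becomes 210 vs 105.
- **Analysis.** Analysis Plan by Study Aim, Aim 1, uses GEE to compare "changes over time in the dichotomous outcomes - PrEP uptake, nPEP uptake" and the other binary outcomes immediately post intervention and at 3, 6 and 9 months. It tests time, arm and their interaction. The default is continuous time, with categorical time if nonlinearity appears.
- **Hypothesis.** H1 under Objectives expects larger improvement over 9 months in the intervention arm.

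No section says what makes a visit a 1, how a participant already on PrEP at entry is scored, or which of the three model terms settles the PrEP question.

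**The concern.** A first prescription is essentially a one-off event. A repeated-measures model needs a rule that turns it into a yes or no at each visit, and three rules are plausible. Someone prescribed PrEP in month 1 who later stops is yes at every visit under ever prescribed, yes once under prescribed since the last visit, and yes then no under current use. The same youth therefore give a rising, a collapsing or a declining curve.

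The wording of H1 and of the analysis plan leans towards arm-by-time, which is the term most sensitive to this choice. If rule and term are chosen after the data are seen, the PrEP result of a primary endpoint is open to selection, and the quoted power may not belong to the test that is reported.

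**Working it through.** **1. The plan's own figure.** Inputs: 24% vs 4%, n = 210 vs 105, alpha 0.05 (two-sided assumed).
- Pooled rate = (210 × 0.24 + 105 × 0.04)/315 = 54.6/315 = 0.1733.
- SE under no difference = √[0.1733 × 0.8267 × (1/210 + 1/105)] = 0.0452.
- SE under the alternative = √(0.24 × 0.76/210 + 0.04 × 0.96/105) = 0.0351.
- Power = Φ[(0.20 − 1.96 × 0.0452)/0.0351] = Φ(3.17) = 0.999.

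The 99% is reproduced for an arm contrast. The printed interval is close to the exact one for 99 successes in 100 runs (94.55 to 99.97). For 990 in 1000 it would be 98.2 to 99.5, so the PrEP run seems to have used about 100 simulations.

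**2. The interaction with the same inputs.** Take two time points, 2% to 24% and 2% to 4%, treated as independent.
- Interaction log OR = ln(0.24/0.76) − ln(0.04/0.96) = 2.03.
- Variance = 1/(210 × 0.24 × 0.76) + 1/(210 × 0.02 × 0.98) + 1/(105 × 0.04 × 0.96) + 1/(105 × 0.02 × 0.98) = 0.026 + 0.243 + 0.248 + 0.486 = 1.003.
- z = 2.03/√1.003 = 2.02, and power = Φ(2.02 − 1.96) = about 0.52.

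A within-person correlation of 0.3 or 0.5 raises this to 0.65 or 0.76. Simulated logistic GEEs (210 vs 105, latent correlation 0.3 and 0.5) gave:
- 69-70% on a logit-linear path over five visits;
- 48-56% on a probability-linear path;
- 24-25% for an immediate step with continuous time;
- about 3% in each direction if rates are flat over the four follow-ups.

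With 300 vs 150 and no attrition, the simulated rising paths gave 67-84%.

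**3. The same youth under different scorings.** From the plan: 2% on PrEP at entry, and 24% vs 4% ever on PrEP by 9 months, that is 22% vs 2% new. Assumed: the timing of starts and, for current use, 40% stopping per interval. The model has four post-intervention visits, continuous time, an independence working correlation and robust SEs.

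| Starts in the four intervals | Scoring | Intervention arm, % at the four visits | Arm-by-time log OR per visit | Significant for / against |
|---|---|---|---|---|
| 70/15/10/5% | Ever prescribed | 17.4, 20.7, 22.9, 24.0 | −0.03 | 18% / 6% |
| | Since last visit | 15.4, 3.3, 2.2, 1.1 | −1.09 | 0% / 46% (26% not estimable) |
| | Current use | 16.6, 13.3, 10.1, 7.2 | −0.26 | 3% / 21% |
| | Cumulative new uptake | 15.4, 18.7, 20.9, 22.0 | −0.29 | 10% / 35% (21% not estimable) |
| Even | Ever prescribed | 7.5, 12.9, 18.4, 24.0 | +0.28 | 51% / 2% |
| | Since last visit | 5.5 at each | +0.04 | 10% / 7% |
| | Current use | 6.7, 9.5, 11.2, 12.2 | +0.27 | 22% / 4% |
| | Cumulative new uptake | 5.5, 11.0, 16.5, 22.0 | +0.07 | 14% / 15% |

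Without the interaction, the arm effect favoured the intervention significantly in about 86-98% of runs under every scoring, counting non-estimable runs as failures.

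**4. Why scoring and deciding term must be fixed together.** Take cumulative new uptake with early starts, and control at 0.5% rising to 2.0%. The risk difference grows from 15.4 − 0.5 = 14.9 points to 22.0 − 2.0 = 20.0 points. The odds ratio falls from (0.154/0.846)/(0.005/0.995) = 36 to (0.22/0.78)/(0.02/0.98) = 14. A logit slope then counts against an intervention whose lead is widening.

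**5. Power on new uptake.** For 22% vs 2%, the pooled rate is 48.3/315 = 0.1533 and the two SEs are 0.0431 and 0.0317. Power = Φ[(0.20 − 1.96 × 0.0431)/0.0317] = Φ(3.65), above 0.99. The chance of no new control uptake is 0.98^105 = 0.12, in which case a logit arm effect cannot be estimated.

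**The case against.** **Only one outcome definition exists.** A reader might infer that the documents hold three rival definitions: a prescription, a start during the study, and a status already at 2%. They do not. The sub-study wording, "Participants who initiate PrEP during the study", is an invitation condition, and the similar phrase under HIV Risk Profile and PrEP Eligibility Assessment selects youth for an adherence test. A 2% starting rate is compatible with prescriptions written before enrolment. This objection stands: the gap is a missing rule, not a contradiction.

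**The reversal is conditional.** It concerns only the arm-by-time slope and needs early starts, plus stopping for current use. Early starts are suggested by the design: a 3-month session period, eligibility screening from the first session, and medication about 3 days after labs and application. But no distribution of start times is given.
- Objectives also lists baseline among the comparison times. In separate runs with 85% early starts and 10% stopping per month, adding baseline cut significance against the intervention from 65% to 9% (since last visit) and from 31% to 4% (current use).
- A front-loaded step is nonlinear, so the plan's own switch to categorical time could apply.

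All of this stands as a limit on the size. It does not supply the missing rule.

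**The 99% is not wrong.** It holds for an arm contrast, and arm is one of the planned tests. That stands too. What is missing is a statement that this contrast decides.

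**Prescription is a legitimate endpoint.** One might want to replace it with receipt of medication. The documents give no reason to. Study nurses dispense in the intervention arm while usual care offers referrals, so a dispensing-based endpoint risks different ascertainment by arm.

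**Conclusion.** The point holds in this form: a component of the primary endpoint has a stated source but no per-visit scoring rule, no handling of the roughly 2% on PrEP at entry (0.02 × 450 = about 9 youth), and no deciding term.

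The firm part needs no assumption about timing: 99% belongs to an arm contrast of 24% vs 4%. At 210 vs 105, arm-by-time has about 24-70% in simulations of paths rising from 2% (52-76% by the two-point approximation). With ever-scoring at the four planned visits it has about 18-51%, depending on when starts occur.

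The conditional part is the sign. With starts concentrated in the session period, the slope was significant against the intervention in 46% of runs under since-last-visit scoring and 21% under current use. With even starts nothing clearly reverses. It would be wrong to conclude that the trial could show the intervention to be harmful for PrEP uptake, or that its PrEP power is inadequate: the arm effect keeps its direction throughout, and an end-of-study comparison is well powered.

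**What to change.** 1. Keep the chart-verified prescription, ascertained by the same rule in both arms. Nurse report has no evident counterpart in controls, who receive the intervention only after the 9-month visit.
2. Score it cumulatively from randomisation: once yes, yes at all later visits.
3. Identify youth already on PrEP at entry and do not count them as new uptake.
4. Make the deciding PrEP result the arm difference in cumulative uptake by the 9-month visit. Express it as a difference in proportions, with a test that remains valid when control events are few or absent. Arm-by-time and current use at each visit become secondary.
5. State that the power figure refers to that contrast, restate the inputs as about 2% vs 22% new uptake if the plan's rates are kept, and report the number of simulation runs.

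The cost is wording in Measures and the analysis plan, a consistent way to record PrEP use at entry and at each visit, and one re-run of the power calculation. The small loss is that youth already on PrEP no longer contribute events. By the calculation above, power for the deciding contrast stays above 99%.

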Sources of Materials.

Baseline and Follow-up Survey Data. 5 Surveys will be collected at baseline, immediate, 3-, 6-, and 9-months post intervention using REDCap online surveys delivered on iPads or accessed remotely by participant smartphone or computer. Surveys will be provided in a quiet, private room at the drop-in center and shelter, and take about 30 minutes each to complete. In cases when a participant prefers to complete their survey at another location, the research assistant will find an agreed upon location to meet up with the youth to complete the survey such as a near-by library or coffee shop. For youth who leave the area during the data collection period, we will create an individualized survey link generated from REDCap. This web-based

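### The Aim 2 power statement (n = 315, f = .11, r = .50, 80%) does not fit its stated correlation and the five planned survey waves, and should be recomputed and restated

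*Combined protocol and SAP*

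**What the plan says.** The statement is in Statistics, under Sample Size and Power Calculations. For the continuous instrument scores of Aim 2, n = 315 is said to give "80% power for the interaction of time and arm in a repeated measures model when the effect size is f= .11", which the plan calls a small effect. The next sentence reads "This calculation assumes a correlation between repeated measures of r = .50".

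Other parts of the plan bear on this:

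- **Sample size and allocation.** "Conservatively assuming an attrition rate of 30% at 9 months, the final sample size will be 315". Because twice as many are randomized to intervention as to control, these split into 210 and 105.
- **Alpha.** The .05 level is given in the Aim 1 power text ("Alpha was set at .05 and the power calculation was conducted using" a simulation package). None is given for Aim 2.
- **Waves.** Sources of Materials says "5 Surveys will be collected at baseline, immediate, 3-, 6-, and 9-months post intervention", and Aim 2 under Objectives lists the same five time points. The Aim 1 analysis sentence names four, "assessed immediately post intervention and at 3-, 6-, and 9-months".
- **Coding of time.** In the Aim 2 analysis, "Time will be treated as a continuous variable unless nonlinearities are present, in which case it will be treated as a categorical variable".

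The Aim 2 power text does not state the number of waves, the definition of f, a sphericity assumption, or whether the interaction tested is a slope or an omnibus term.

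**The concern.** A reader takes r = .50 to be one of the inputs that produced 80%. With r as an input, the usual repeated-measures calculation gives far more than 80% at f = .11. A calculation that does give about 80% leaves r out and counts four waves rather than five. The two sentences therefore do not describe one identifiable calculation.

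This is the only power statement for Aim 2. As printed, it does not tell a reader what difference in symptom score, substance use or homeless days the trial can detect, and the label of a small effect cannot be checked.

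**Working it through.** **Inputs.** N = 315, two arms (210 and 105), f = .11, r = .50, all from Sample Size and Power Calculations. Alpha .05 is carried over from Aim 1 (assumption). The number of waves m is 5 by design; m = 4 is also tried because the Aim 1 analysis names four. Data are taken as complete on 315 participants. Sphericity is assumed, which is what one common correlation with equal variances implies.

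**Test.** Noncentral F for time by arm, with df1 = m − 1, df2 = (N − 2)(m − 1) = 313(m − 1), and noncentrality λ.

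**Closest match to the plan's 80%: f from partial eta-squared.** Here λ = f²(N − 2)(m − 1).

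- m = 4: λ = .0121 × 313 × 3 = 11.36, power 81.6%. Power is exactly 80% at f = .108, which rounds to .11.
- m = 5: λ = .0121 × 313 × 4 = 15.15, power 89.3%. Power is 80% at f = .098.

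r does not appear in this formula.

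**f scaled to the total SD.** Here r enters: λ = f² N m/(1 − r).

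- m = 4: λ = .0121 × 315 × 4/.50 = 30.49, power 99.85%. Power is 80% at f = .066.
- m = 5: λ = .0121 × 315 × 5/.50 = 38.11, power 99.97%. Power is 80% at f = .062.
- m = 2 and m = 3 give 97.3% and 99.3%.
- The lowest possible sphericity correction still leaves 88.8% (m = 4) and 86.8% (m = 5).
- Simulation with 210 versus 105 and a linear interaction gave 99.9% (m = 4) and 99.97% (m = 5).

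**f scaled to the within-subject error SD.** With λ = f² N m, power is 92.0% (m = 4) and 95.4% (m = 5).

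**Rounding of f.** At five waves the lowest value that rounds to .11 is .105. It gives 86.0% (partial eta-squared), 93.4% (error SD) and 99.9% (total SD). Rounding does not explain the gap.

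**The two main scales compared.** Equating the noncentralities at r = .50 gives f(total SD) = f(partial) × √[313(m − 1)(1 − r)/(315m)].

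- m = 4: factor 0.610, so .11 becomes .067.
- m = 5: factor 0.630, so .11 becomes .069.

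**As a score difference.** Suppose the arms diverge linearly from zero at baseline over five equally spaced waves, reaching d SD at 9 months. The centred differences are d × (−.5, −.25, 0, .25, .5), with mean square .125d². The 2:1 split contributes (2/3)(1/3) = 2/9. So f(total SD) = d√(.125 × 2/9) = 0.1667d.

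- f = .11 on the total-SD scale: .11/.1667 = 0.66 SD.
- f = .11 from partial eta-squared: .069/.1667 = about 0.42 SD.
- 80% power for the 4-df omnibus test: .0617/.1667 = 0.37 SD.
- 80% power for the default 1-df slope: the SE of d is 4 × √[(.50/10)(1/210 + 1/105)] = 0.107, and 2.80 × 0.107 = 0.30 SD.

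**The case against.** The strongest defence is that the plan never defines f or counts the waves, so no single power follows from what it prints. A recognised definition with four waves reproduces the figure to rounding (80% at f = .108). On that scale r is absorbed into f, so quoting r = .50 can be legitimate: it is what converts f into a score difference. The values f = .11 on one scale and about .066 on the other can describe almost the same effect.

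Much of this stands, and it rules out several stronger conclusions that a reader might draw:

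- **That the true power is over 99%, not 80%.** This holds only for the total-SD definition with three or more waves.
- **That the detectable effect is overstated 1.7 to 1.8 times, or that 100 to 114 participants would do.** Both rest on the same definition. On the other scale with four waves, most of the factor is a change of units (.11/.067 = 1.64).
- **That the r = .50 sentence is false and should go.** It may be needed to interpret f.

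Some unstated choices also bring five waves near 80%. The partial eta-squared version with a sphericity correction of .75 gives 81.6%, and the error-SD version with a correction of .50 gives 79.3%. A 1-df test with λ = N f²/(1 − r) = 7.62 gives 78.6% and does use r, but f must then be defined on a single normalised time contrast, √5 times the total-SD f at five waves. The plan mentions neither a correction nor such a definition, and a single common r implies no correction.

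The defence does not rescue the text as written. The four-wave match makes no direct use of r and omits one of the five waves listed for Aim 2.

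**Conclusion.** The point holds in a limited form. Under the two usual definitions of f, with sphericity and alpha .05, the stated n, f, r and power do not agree for five waves: power at f = .11 is 89.3% or 99.97%. Only the partial eta-squared definition with four waves comes near 80% (81.6%), and r = .50 is not an input there. Which calculation was run cannot be recovered from the plan.

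In score terms, f = .11 could mean about 0.42 or 0.66 SD at 9 months, while the default slope test would reach 80% power at about 0.30 SD. These figures assume linear divergence, equally spaced waves, r = .50 between all waves and complete data on 315.

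The discrepancy is conservative. A reader might infer that Aim 2 is underpowered or that the trial is the wrong size, but the documents do not support either. The Aim 2 calculation takes 315 as given rather than setting it, and the primary endpoint is defined by the Aim 1 outcomes. This is a minor correction to a stated figure.

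**What to change.** Recompute Aim 2 power for the planned analysis: five waves, 210 versus 105, r = .50, alpha .05, and the time-by-arm term actually tested (a 1-df slope by default, with the categorical version as a second line if wanted). Then replace the two sentences with the power or detectable effect. State the definition of f, the number of waves, how r was used and the sphericity assumption. Preferably express the effect as an SD difference at 9 months.

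Do not simply delete the r = .50 sentence, because r is needed to turn f into a score difference. If the four-wave calculation was intended, say so and explain why one planned wave is left out.

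The cost is one recalculation and two revised sentences, with no change to the design, sample size or data collection.
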